Central Pharmacokinetic

Laboratory:

Bioanalytical Laboratory "Exacte Labs"

Legal / mailing address: [name].

[contact]

CONFIDENTIAL Page 5 of 88

INVESTIGATIONAL SITES

List of Investigational Sites participating in this clinical study (name, address and telephone number of each site; name and title of the investigators) is provided in a separate List of Investigational Sites and Principal Investigators.

CONFIDENTIAL Page 6 of 88

DESCRIPTION OF THE PROTOCOL CHANGES

The changes introduced into the Protocol by Amendment No. 4 dated 26 April 2017 are listed below:

Appendix 1 contains Intensive Care Unit admission criteria that have been corrected on the basis of the "Clinical guidelines for the diagnosis, treatment, and prevention of severe community-acquired pneumonia in adult patients of 2014" (referred to further in the protocol changes description as the "2014 Clinical Guidelines"). These criteria have been brought into agreement with the Infectious Diseases Society of America / American Thoracic Society criteria referenced by the 2014 Clinical Guidelines.

Section 11.5 now contains clarified requirements for the registration of pregnancies in the course of the study.

Sections 12.1 and 12.2 contain clarified requirements for the enrollment of subjects in the Clinically Evaluable (CE) population.

Section 13.3 now provides information on the financing and insurance of the study.

Minor formatting changes and correction of misprints in the protocol were performed as well.

The principal changes introduced into the Protocol by Amendment No. 3 dated 26 December 2016 are listed below.

The following changes were made in the inclusion criteria:

- Inclusion criterion No. 2 was modified: the maximum age of patients that can be enrolled in the study was increased to 70 years inclusive. This change was due to a significant proportion of such patients in the overall population of patients admitted to hospital with a diagnosis of "community-acquired pneumonia", and was aimed to enlarge the study population.
- Inclusion criterion No. 3 was clarified (the need to meet the requirements of Appendix 1 "Criteria for hospitalization" was again underlined).
- For Inclusion criterion No. 4, a clearer definition of required symptoms / signs was included: the terms "dyspnea" and "rigors" were excluded to avoid misunderstanding.

The following change was made in the exclusion criteria:

• For Exclusion criterion No. 4, a clearer definition of QT prolongation was included: *QTc(F)* interval more than 450 ms.

In the "Contact information" section, information on the Central Microbiological Laboratory and the Central Pharmacokinetic Laboratory was added.

Section 8.6 "Blinding" now contains a modified description of the package labeling, which will allow masking of blinding packages right at the investigational sites for more convenience of the investigational site personnel.

CONFIDENTIAL Page 7 of 88

Section 8.7 "Prior and concomitant therapy" now contains a clarification that the eCRF documents information on previous drugs and treatments used from the onset of community-acquired pneumonia until the enrollment in the study (signing of the Informed Consent Form).

Section 9.1 "Schedule of study procedures" now includes, in the interests of study subjects, clarified requirements for the time frame of Visit 3, which should be conducted at least 24 hours after the last dose of the study drug.

The description of the screening procedures and Sections 10.3.4, 10.3.5, 10.3.6 now include information that the Investigator may use laboratory test results obtained at the laboratory of the investigational site within 24 hours of study enrollment (Signing of the Informed Consent Form) if he / she considers that available data are sufficient to permit a decision on whether the subject meets the selection criteria. In this case, another blood sampling procedure has to be conducted in the period from the signing of the Informed Consent Form to the start of treatment in order to evaluate all other laboratory parameters that have to be determined on Day 1 in accordance with the study protocol. This amendment was done in the interests of study subjects, in order to rule out more unnecessary material collection procedures, as well as to shorten the time to start of treatment.

The description of the screening procedures (9.2.1) now provides clarifying information that prior therapy should be evaluated *for the 30 days preceding the Visit* and treatment, *from the onset of community-acquired pneumonia*.

For all study visits including an ECG recording (Visit 1 "Screening procedures", Visit 2 "Switch to oral therapy", Visit 3, Visit 4), an opportunity was added, for more convenience of patients and investigators, to have an ECG recording not only before the blood sampling procedure, but also 30 minutes after it.

The description of the Visit 2 procedures (9.2.2) now provides clarifying information that, in the event intravenous therapy is prolonged, the overall duration of treatment within this study will not exceed 14 days.

Section 10.2.1 "Chest X-ray / Chest Computed Tomography" now includes clarifying information that *only one radiological method (X-ray imaging only or CT imaging only for all visits) should be used for a patient throughout the study* to ensure unified and improved quality of analysis.

Section 10.3.7 "Documentation of adverse events" now contains clarified requirements for the documentation of adverse events.

Section 11.1.1 "Adverse event (AE)" now provides clarifying information in order to improve the adverse event reporting procedure: any worsening of symptoms of the primary disease (as compared with estimates made during the screening procedures) should also be registered as an AE; there is now also information that the Investigator will record all available information on each occurring SAE in the source documentation.

The title of Section 11.4 "Management of Non Serious Adverse Events (NSAEs) and/or laboratory abnormalities" was changed to 11.4 "Management of adverse events not classified as serious". A requirement was also included to record information about adverse events in the source documentation.

Clarifying information was included in Appendix 1:

CONFIDENTIAL Page 8 of 88

- Clearer criteria for preferred in-patient treatment and for hospitalization in an intensive care unit were included.
- One of the criteria for hospitalization in an intensive care unit was better defined: Respiratory rate ≥ 30 movements per minute.

Minor formatting changes and correction of misprints in the protocol were performed as well.

The changes introduced into the Protocol by Administrative Amendment No. 1 dated 17 March 2016:

The mailing address of the Study Sponsor was changed to [name].

Section 8.9 "Treatment compliance" now mentions that the *volume* (mL) of the infusion (instead of the dose) will be recorded in the eCRF.

1 ABBREVIATIONS

ADR	Adverse drug reaction
AE	Adverse event/experience
ALP	Alkaline phosphatase
ALT	Alanine aminotransferase (alanine transaminase)
AST	Aspartate aminotransferase (aspartate transaminase)
BLNAR	β-lactamase negative ampicillin-resistant
CAP	Community-acquired pneumonia
CAPRIE	Community-Acquired Pneumonia Recovery in the Elderly
C. pneumoniae	Chlamydophila pneumoniae
CNS	Central nervous system
CRA	Clinical research associate
CRO	Contract research organization
CT	Computed tomography
DBP	Diastolic blood pressure
DNA	Deoxyribonucleic acid
DRSP	Drug-resistant S.pneumoniae
eCRF	Electronic Case Report Form
ECG	Electrocardiogram
ESR	Erythrocyte sedimentation rate
GCP	Good Clinical Practice
GGTP	Gamma-glutamyl transpeptidase
GI	Gastrointestinal system
H. influenzae	Haemophilus influenzae
ICF	Informed consent form
ICH	International Council on Harmonisation
IEC	Independent Ethics Committee
IMP	Investigational Medicinal Product
INN	International Non-proprietary Name
ISF	Investigator Site File
i.v.	Intravenous
IWRS	Interactive Web Response System
K. pneumoniae	Klebsiella pneumoniae
L. pneumophila	Legionella pneumophila
LRTI	Lower respiratory tract infection
MedDRA	Medical Dictionary for Regulatory Activities

CONFIDENTIAL Page 14 of 88

MRSA	Methicillin-resistant Staphylococcus aureus
M. pneumoniae	Mycoplasma pneumoniae
NSAE	Non Serious Adverse Events
NFQ	Non-fluorinated quinolone
PISP	Penicillin-intermediate S. pneumonia
PRSP	Penicillin-resistant S. pneumonia
P. aeruginosa	Pseudomonas aeruginosa
рН	Hydrogen ion concentration
PQ	Cardiac PQ interval
QRS	Cardiac QRS interval
QT	Cardiac QT interval
QTc	Cardiac QT interval corrected for heart rate
SAE	Serious Adverse Event/experience
S. aureus	Staphylococcus aureus
SBP	Systolic blood pressure
SD	Standard deviation
SOPs	Standard Operating Procedures
S. pneumoniae	Streptococcus pneumoniae
SUSAR	Suspected Unexpected Serious Adverse Reaction
TMP-SMX	Trimethoprim-sulfamethoxazole
ULN	Upper limit of normal
WBC	White blood cell
WHO	World Health Organization

Page 15 of 88

2 SYNOPSIS

Title of Study:	An international, multicenter, randomized, double-blind, double-		
	dummy, two-way, parallel group, controlled study to compare		
	the efficacy and safety of intravenous and oral Nemonoxacin		
	versus Tavanic [®] in adult patients with community-acquired		
	pneumonia.		
Protocol code:	CJ01060044		
Sponsor:	R-Pharm JSC		
Medical condition	Community-acquired pneumonia (CAP)		
or disease under			
investigation:			
Objectives:	Primary objective		
J	• To evaluate the clinical efficacy of treatment with Nemonoxacin compared with Tavanic [®] in patients with CAP.		
	Secondary objectives		
	To evaluate the clinical efficacy of treatment with intravenous Nemonoxacin compared with intravenous Tavanic [®] in patients with CAP		
	• To assess the safety of treatment with Nemonoxacin compared with Tavanic [®] in patients with CAP		
	To assess the pharmacokinetic parameters of intravenous Nemonoxacin in adult patients with CAP		
	• To evaluate the microbiological efficacy of treatment with Nemonoxacin compared with Tavanic [®] in patients with CAP.		
Study design:	This is an international, multicenter, randomized, double-blind, double-dummy, controlled, parallel group study of		
	efficacy and safety.		
	Treatment-naive patients with community-acquired		
	pneumonia (non-nosocomial pneumonia) and patients with		
	treatment failure will be screened and if eligible will be		
	randomized to receive either treatment with Nemonoxacin or		
	Tavanic [®] in a ratio of 1:1.		
	Patients will stay at hospital (non-intensive care unit) and		
	receive daily i.v. treatment with either invesigational product		
	(Nemonoxacin 500 mg (250 ml), solution for infusion) with		
	Placebo (100 ml), solution for infusion, or comparator (Tavanic®		
	500 mg (100 ml), solution for infusion) with Placebo (250 ml),		
	solution for infusion, for at least 3 days. The i.v. treatment may		
	be prolonged by decision of investigator until and including Day		
	7 of the study.		
	Thus the investigator will switch a patient from i.v. to		

CONFIDENTIAL Page 16 of 88

oral therapy at Day 4(8) of the study if the specific criteria of clinical stability are achieved. The treatment will be continued with appropriate oral therapy. If the patient receives i.v. therapy with Nemonoxacin he/she will continue oral therapy with Nemonoxacin 250 mg, 2 capsules per day. If the patient receives i.v. therapy with Tavanic[®] he/she will continue oral therapy with Tavanic[®] 250 mg, 2 over-encapsulated film coated tablets per day.

The duration of oral therapy will be judged by investigator and oral therapy will last until and including Day 7(14) of the study.

The study includes 5 visits:

- 1. Visit 1 (Screening /randomization/ intravenous therapy, Days 1-3(7) of the study)
- 2. Visit 2 (Switch to oral therapy /oral therapy, Days 4(8)-7(14) of the study)
- 3. Visit 3 (End of treatment visit, within 1-2 days after the last dose)
- 4. Visit 4 (Test of cure visit, within 7-9 days after the last dose)
- 5. Visit 5 (Long-term follow-up visit; within 21-23 days after the last dose).

Number of Subjects:

A total of 342 eligible patients (171 patients per test group) will be enrolled and randomized in the study. Presumably screening of 382 patients will allow randomization of 342 patients.

Inclusion Criteria:

- 1. Written informed consent obtained from the patient.
- 2. Female and male patients aged between 18 and 70 years inclusive.
- 3. Patients with moderate to severe community-acquired pneumonia who need inpatient treatment (correspodence to at least one of the criteria for hospitalization / preferred hospitalization described in the Appendix 1 of this protocol) but do not need ICU treatment (in case of correspondence to at least one «major» or three «minor» criteria for hospitalization in intensive care unit described in Appendix 1 of this protocol, patient should not be enrolled in the study).
- 4. The presence of at least 3 of the following symptoms/signs:
 - Cough
 - Purulent sputum production
 - Tachypnea (respiratory rate > 24 breaths/minute)
 - Chills
 - Fever (rectal/ tympanic temperature ≥ 38.5°C or axillary/ oral/ cutaneous temperature ≥ 38.0°C)
 - WBC count of $\geq 10.0 \text{ x } 10^9/\text{L}$ or $\geq 15\%$ immature

CONFIDENTIAL Page 17 of 88

neutrophils (bands; regardless of peripheral WBC count).

- 5. Radiological evidence of (a) new infiltrate(s) consistent with bacterial pneumonia at baseline.
- 6. Treatment-naive patients or patients who have received single dose of a short-acting antibacterial drug within 24 hours of enrollment or patients with treatment failure who have received antibiotics (with the exception of quinolones or fluoroquinolones) for less than 72 hours.
- 7. Consent to use contraception during participation in the study (for women of childbearing potential and men).

Exclusion Criteria:

- 1. Known hypersensitivity to quinolones, fluoroquinolones or any of the excipients.
- 2. Female patients who are pregnant or nursing.
- 3. History of tendon disease/disorder related to quinolone treatment.
- 4. Known congenital or documented-acquired QT/QTc(F) prolongation on ECG (QTc(F) interval more than 450 ms); concomitant use of drugs, reported to increase the QT interval; uncorrected hypokalaemia and uncorrected hypomagnesemia; clinically relevant bradycardia; clinically relevant heart failure with reduced left-ventricular ejection fraction; previous history of symptomatic arrhythmias.
- 5. History of bronchiectasis, cystic fibrosis, bronchial obstructions excluding chronic obstructive pulmonary disease.
- 6. History of epilepsy and/or history of psychotic disorder.
- 7. Patients with history of myasthenia gravis.
- 8. Patients with diabetes mellitus.
- 9. Known glucose-6-phosphate dehydrogenase deficiency.
- 10. Active hepatitis or decompensated cirrhosis.
- 11. Alanine transaminase or aspartate transaminase increase > 3 fold ULN.
- 12. Patients with creatinine ≥ 1.1 fold ULN.
- 13. Patients requiring concomitant systemic or inhaled antibiotics (e.g., tobramycin).
- 14. Known or suspected active tuberculosis or endemic fungal infection.
- 15. Concomitant immunosuppressive therapy including a long-term (more than 2 weeks) treatment with oral or intravenous glucocorticoids at doses of 20 mg and higher of prednisone daily or an equivalent dose of other glucocorticoids.
- 16. Patients known to have HIV-positive status or AIDS or known to have other disease that seriously affects the

CONFIDENTIAL Page 18 of 88

Investigational	 immune system such as active haematological or solid organ malignancy, or splenectomy. 17. History of drug or alcohol abuse. 18. Patients have received quinolones or fluoroquinolones within 14 days before enrollment. 19. Previous enrolment in this study or participation in another study within the previous 4 weeks. 20. Patients with any severe medical condition as determined by medical history that, in the opinion of the investigator, does not allow the patient to carry out all planned procedure of the protocol. Investigational product 1: Nemonoxacin 500 mg (250 ml),
products, dosage and mode of administration:	solution for infusion. Dosage and mode of administration: 500 mg (250ml) daily administered as single intravenous infusion over 90-110 minutes.
	• Investigational product 2: Nemonoxacin 250 mg, capsules. Dosage and mode of administration: a dose of 500 mg (two 250 mg capsules) will be administered orally once a day.
Comparators, dosage and mode of administration:	 Comparator 1: Tavanic[®] 500 mg (100 ml), solution for infusion. Dosage and mode of administration: 500 mg (100 ml) daily administered as single intravenous infusion over a minimum duration of 60 minutes. Comparator 2: Tavanic[®] 250 mg, film coated tablets. Each tablet is placed into a capsule shell (over-
	encapsulated) for blinding purposes. Dosage and mode of administration: a dose of 500 mg (two 250 mg over-encapsulated film coated tablets) will be administered orally once a day.
Placebo, dosage and mode of administration:	 Placebo (100 ml), solution for infusion. Dosage and mode of administration: 100 ml of solution will be administered daily as single intravenous infusion over a minimum duration of 60 minutes after the infusion of Nemonoxacin, solution for injection. Placebo (250 ml), solution for infusion.
	Dosage and mode of administration: 250 ml of solution will be administered daily as single intravenous infusion over 90-110 minutes before the infusion of Tavanic [®] , solution for infusion.
Duration of treatment:	For each patient treatment duration will be approximately $7 - 14$ days.

CONFIDENTIAL Page 19 of 88

Endpoints:

Efficacy endpoints:

Primary endpoint:

• Proportion of patients with clinical success as judged by the investigator at the test of cure visit (Visit 4).

Secondary endpoints:

- Proportion of patients with clinical success as judged by the investigator at the Visit 2 (switch to oral therapy) and Visit 3
- Proportion of patients with infection relapse at Visit 5
- Time to switch therapy from i.v. to oral therapy
- Need for other antibiotic treatment
- Proportion of patients with microbiological responses at the Visit 2 (switch to oral treatment), Visit 3 and Visit 4.

Safety endpoints:

- Adverse events
- Changes in vital signs
- Clinical laboratory results
- ECG results
- Physical examination results.

PK parameters:

- C_{max}
- $C_{22.5h}$
- AUC_{0-22.5}
- AUC_{0-inf}
- CL
- \bullet V_{ss}
- T_{1/2}

Statistical methods:

Samples size calculation

The primary efficacy objective is to show that Nemonoxacin is not inferior to Levofloxacin (Tavanic®) for the treatment of CAP, on the basis of the primary efficacy endpoint clinical success at Visit 4 (Test of cure visit) in the mITT population. The sample size calculation for this endpoint is based on assuming a clinical success rate of 82% in the treatment and in the active control group, and an eligibility of 80% of the randomized patients for mITT population. Non-inferiority margin is chosen to be 15% (i.e., δ = -15%), a one-sided significance level α is set at 5%. Then, to achieve power of 80%, the sample size for equal allocation is estimated as 171 randomized patients in each group (342 patients totally) that provides about 137 patients in each group (274 patients totally) in the mITT population.

Presumably screening of 382 patients will allow randomization of 342 patients.

CONFIDENTIAL Page 20 of 88

Statistical methods

Primary efficacy analysis

The percentage and the number of patients with different categories of clinical response ("clinical success", "clinical failure", "indeterminate") will be summarized by treatment group in mITT and CE populations for Visits 2 (switch to oral therapy), Visit 3 and Visit 4.

The percentage of patients with clinical success (as judged by the investigator) at the test of cure Visit 4 is defined as primary endpoint variable.

In regards to efficacy for CAP, non-inferiority of Nemonoxacin compared to Tavanic® will be evaluated for clinical response by using a one-sided 95% confidence interval for the difference in the primary efficacy endpoint (investigational product minus comparator). Non-inferiority of Nemonoxacin will be stated if the lower boundary of the estimated one-sided 95% confidence interval for the difference in the clinical success rate of Nemonoxacin and Tavanic® is above -15% the Farrington-Manning test.

The primary analysis will be performed in the mITT population.

If non-inferiority is shown, a test on superiority will be performed in addition using the two-sided 95% confidence interval. The test on superiority is significant, if the lower two-sided 95% confidence interval limit is above "0".

Secondary efficacy analyses

As a supportive analysis, the primary efficacy endpoint will be analyzed in the CE population using the same method as that used for the primary efficacy analysis.

For secondary efficacy analyses, the clinical success rates of the patients in the mITT and CE populations at Visits 2 and 3 as well as the number (proportion) of patients who needed other antibiotic treatment (treatment failure) will be analyzed using a two-sided 95% confidence interval (equality test) calculated based on the same statistical test as for the primary analysis.

Additionally, the results of statistical comparison of the clinical success rates using the logistic regression will also be provided.

Microbiological efficacy endpoints will include microbiological success rates evaluated per each patient and by identified pathogens in b-mITT and BE.

The percentage and the number of patients with microbiological success and failure will be summarized by visit and treatment group. Microbiological success is defined as the

CONFIDENTIAL Page 21 of 88

assessments of eradication and presumed eradication. Other results of assessments (excluding unevaluable) will be regarded as microbiological failure. The difference between microbiological success rates and its CI will be calculated using the same method as that used for the secondary efficacy endpoints.

The percentage and number of the baseline-identified strains (sputum and blood culture) with microbiological success and failure will be summarized by visit and treatment group. The frequency of each category and sample source (sputum and blood culture) will be presented separately and by treatment group. Microbiological data by identified pathogens will be analyzed descriptively.

Time to switch therapy from i.v. to oral therapy will be evaluated using the Kaplan – Meier survival analysis method and compared by log-rank test between treatment groups. The Kaplan-Meier curves will be presented graphically.

Safety evaluation

Safety evaluation will include assessment of AEs, vital signs, ECG and physical examination data and laboratory tests in the safety population. All safety statistical analyses will be performed descriptively.

Pharmacokinetic parameters

The non-compartment method will be used to analyze the Nemonoxacin concentration-time data after the first intravenous Nemonoxacin infusion in adult patients with CAP.

The following pharmacokinetic parameters will be estimated from the measured concentrations: the peak drug concentration (C_{max}), 22.5-h drug concentrations ($C_{22.5h}$), areas under the concentration-time curve from 0 to 22.5 h, and 0 h to infinity ($AUC_{0-22.5}$, $AUC_{0-\infty}$), total systemic clearance (CL), volume of distribution at steady state (V_{ss}), and terminal elimination half-life ($T_{1/2}$).

CONFIDENTIAL Page 22 of 88

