12 STATISTICAL METHODS

12.1 Analysis populations

The following populations will be identified for the statistical analyses:

- Randomized Population (RP): All subjects who were screened and randomized
- Intent-to-Treat Population (ITT): All subjects in the RT population who received at least one complete dose of the drug (Nemonoxacin or Tavanic[®])
- Modified Intent-to-Treat (mITT): Subjects in the ITT population who met the minimal disease criteria (inclusion criteria 3 and 4), and was evaluated for clinical efficacy at least once
- Clinically Evaluable (CE): Per-Protocol subjects in the mITT population (i.e. patients without protocol violations and without a clinical response of "Indeterminate" in the mITT population)
- Bacteriological mITT (b-mITT): Subjects in the mITT population whose bacterial culture yielded at least one baseline bacterial isolate
- Bacteriologically Evaluable (BE): patients in the CE population who had at least one baseline bacterial isolate
- Safety Population (SP): All subjects who received at least one complete dose of the study drug (Nemonoxacin or Tavanic®) and underwent at least one safety evaluation would be included in this data population for safety analysis
- Pharmacokinetic population (PK-C): All subjects who were included in PK study and who had at least 1 measured concentration value.

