12.6.2 Primary efficacy analysis

The percentage and the number of patients with different categories of clinical response ("clinical success", "clinical failure", "indeterminate") will be summarized by treatment group in mITT and CE populations for Visit 2 (switch to oral therapy), Visit 3 and Visit 4.

The percentage of patients with clinical success (as judged by the investigator) at the test of cure Visit 4 is defined as primary endpoint variable.

In regards to efficacy for CAP, non-inferiority of Nemonoxacin compared to Tavanic[®] will be evaluated for clinical response by using a one-sided 95% confidence interval for the difference in the primary efficacy endpoint (investigational drug minus comparator). Non-inferiority of Nemonoxacin will be stated if the lower boundary of the estimated one-sided 95% confidence interval for the difference in the clinical success rate of Nemonoxacin and Tavanic[®] is above -15% the Farrington-Manning test.

CONFIDENTIAL Page 65 of 88

The primary analysis will be performed in the mITT population.

If non-inferiority is shown, a test on superiority will be performed in addition using the two-sided 95% confidence interval. The test on superiority is significant, if the lower two-sided 95% confidence interval limit is above "0".

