12.6.3 Secondary efficacy analyses

As a supportive analysis, the primary efficacy endpoint will be analyzed in the CE population using the same method as that used for the primary efficacy analysis.

For secondary efficacy analyses, the clinical success rates of the patients in the mITT and CE populations at Visit 2 (switch to oral therapy) and Visit 3 as well as the number (proportion) of patients who needed other antibiotic treatment (treatment failure) will be analyzed using a two-sided 95% confidence interval (equality test) calculated based on the same statistical test as for the primary analysis.

Additionally, the results of statistical comparison of the clinical success rates using the logistic regression will also be provided.

Time to switch therapy from i.v. to oral therapy will be evaluated using the Kaplan – Meier survival analysis method and compared by log-rank test between treatment groups. The Kaplan-Meier curves will be presented graphically.

Microbiological efficacy endpoints will include microbiological success rates evaluated per each patient and by identified pathogens in b-mITT and BE.

The percentage and the number of patients with microbiological success and failure will be summarized by visit and treatment group. Microbiological success is defined as the assessments of eradication and presumed eradication. Other results of assessments (excluding unevaluable) will be regarded as microbiological failure. The difference between microbiological success rates and its CI will be calculated using the same method as that used for the secondary efficacy endpoints.

The percentage and number of the baseline-identified strains (sputum and blood culture) with microbiological success and failure will be summarized by visit and treatment group. The frequency of each category and sample source (sputum and blood culture) will be presented separately and by treatment group. Microbiological data by identified pathogens will be analyzed descriptively.

Microbiological efficacy evaluation

Based on the results of culture (bacteriological) study the microbiological response will be assessed. Microbiological response is defined as:

- 1. Eradication (admission pathogen[s] is absent),
- 2. Presumed eradication (if no material available for culture because of clinical success)
- 3. Persistence (admission pathogen[s] is present),
- 4. Presumed persistence (no material available for culture for patients with clinical failure),

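### The superiority test names no analysis set other than mITT, and the protocol assigns no efficacy analysis to all randomised patients; if mITT exclusions differ by arm and are mostly non-successes, false superiority becomes much more likely.

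*Combined protocol and SAP*

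**What the plan says.** Section 12.6.2 states: "The primary analysis will be performed in the mITT population". The superiority step comes next, there and in the Synopsis: "If non-inferiority is shown, a test on superiority will be performed in addition using the two-sided 95% confidence interval". It succeeds "if the lower two-sided 95% confidence interval limit is above" zero. No set is named for it, so the natural reading is mITT.

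Section 12.1 defines mITT as: "Subjects in the ITT population who met the minimal disease criteria (inclusion criteria 3 and 4), and was evaluated for clinical efficacy at least once". ITT itself requires one complete dose. The sample-size text assumes "an eligibility of 80% of the randomized patients for mITT population", which is about 137 of 171 per arm.

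The only other set given for this endpoint is in section 12.6.3: "As a supportive analysis, the primary efficacy endpoint will be analyzed in the CE population". CE is a subset of mITT, so it cannot bring back patients whom mITT has already left out.

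Section 12.1 also lists "Randomized Population (RP): All subjects who were screened and randomized", together with ITT. Neither the Synopsis nor section 12.6 assigns an efficacy analysis to them. Section 12.5 leaves missing-data rules to a separate statistical analysis plan, which section 12.9 says will be finalised before the database is closed.

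**The concern.** A superiority claim says that treatment caused the difference, and only the comparison of patients as randomised protects that inference. mITT membership rests on three kinds of condition:

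- **Inclusion criteria 3 and 4** are baseline facts that treatment cannot change.
- **One complete dose** is settled after randomisation. A patient whose first infusion is stopped and who receives no later complete dose leaves ITT, and so mITT. Section 3.3.2.1 reports local administration-site reactions in 27 of 68 and rash in 13 of 68 after intravenous nemonoxacin in phase I. All were mild, so this shows a route to imbalance and not a rate.
- **One efficacy evaluation** is also settled after randomisation. The first scheduled response assessment is on Day 4(8) (section 10.2.2). A patient withdrawn earlier enters mITT only if an early-termination assessment is obtained, and section 7.3 asks for effort but cannot guarantee it.

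Patients lost by the last two routes are unlikely to have been successes on study drug. If one arm loses more of them, its mITT success rate rises without any benefit from treatment. The analyses set out in the protocol would not show this.

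**Working it through.** **Inputs from the documents.** 171 randomised per arm (342 in total); 80% assumed in mITT; success rate 82% in each arm; superiority if the two-sided 95% lower limit exceeds 0; Farrington-Manning method.

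**The plan's own step.** 171 × 0.80 = 136.8, so about 137 per arm and 274 in total, as stated. Exclusions number 342 − 274 = 68. (The 137 does not follow from the stated margin, alpha and power, which give about 82 to 84 per arm. That is a separate matter and does not affect this check.)

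**Assumptions added here.** Successes in mITT: 0.82 × 137 ≈ 112 per arm. All excluded patients are non-successes, so true success is 112/171 = 65.5% in both arms.

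**1. Illustration.** Let 42 be excluded on nemonoxacin and 26 on Tavanic (total 68; 25% and 15%).

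- mITT: 112/129 = 86.8% versus 112/145 = 77.2%, a difference of 9.6 points.
- At a difference of zero the Farrington-Manning variance uses the pooled rate 224/274 = 0.8175. SE = √[0.8175 × 0.1825 × (1/129 + 1/145)] = 0.0467, so z = 0.0958/0.0467 = 2.05, above 1.96.
- Inverting the score test gives a 95% interval of +0.4 to +18.6 points (Wald lower limit +0.6). Superiority would be declared.
- One step less imbalance, 41 versus 27 (112/130 versus 112/144), gives a lower limit of −0.8. With 68 exclusions and 112 successes per arm, 42 versus 26 is therefore the threshold.
- All randomised: 112/171 versus 112/171, difference 0, 95% interval −10.0 to +10.0. No superiority.

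**2. Error rate when the arms are truly equal.** If every excluded patient is a non-success and a fraction e is excluded, the expected mITT rate is 0.655/(1 − e). Normal approximation: P(false superiority) ≈ Φ(difference/SE − 1.96).

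| Excluded, nemonoxacin vs Tavanic | Expected mITT rates | Spurious difference | SE | Φ(·) | Simulated (200,000 runs) |
|---|---|---|---|---|---|
| 20% vs 20% | 81.9% vs 81.9% | 0 | – | 2.5% | 2.5–2.6% |
| 22% vs 18% | 84.0% vs 79.9% | 4.1 points | 4.64 | Φ(−1.08) = 14% | 14% |
| 25% vs 15% | 87.3% vs 77.1% | 10.3 points | 4.56 | Φ(0.29) = 62% | 60–62% |

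The simulated ranges cover the pooled and unpooled tests.

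**3. Exclusions unrelated to outcome.** With 82% success and random exclusion, the simulated error is 2.5–2.6% at 20% in both arms and 2.5–2.8% at 25% versus 15%. Imbalance without a link to outcome does little harm.

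**4. How often chance gives the imbalance in step 1.** With a true 20% exclusion rate in both arms, an excess of 16 or more on nemonoxacin has a probability of about 1.8%.

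**5. Effect on non-inferiority.** With the same 42 and 26 exclusions, 95/129 versus 112/145 has a one-sided 95% lower limit of −12.2 points, which passes the 15-point margin. Over all randomised patients, 95/171 versus 112/171 gives −18.5, which fails.

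**The case against.** The strongest reply is that the harmful case needs a lot to go wrong, and that the protocol works against it. The trial is double-blind. Dosing starts in hospital on Day 1 and is supervised, so few patients should miss a complete dose. Section 7.3 asks for early-termination procedures, which include a response assessment. Table 10-1 makes additional antibiotic therapy, or death from pneumonia, a clinical failure. Many early failures should therefore be evaluated once and enter mITT. A patient who is indeterminate at Visit 4 leaves CE, not mITT. If baseline exclusions were equal, the illustration needs 16 net nemonoxacin non-successes (16/171, over 9% of the arm) with no evaluation at all. All of this stands. It lowers the likely size of the bias but does not remove the route.

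Four stronger readings are tempting, and the documents do not support them:

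- *Unequal exclusions alone create superiority.* They do not; step 3 shows that a link to outcome is also needed.
- *The arms in the illustration cured equal numbers.* That holds only by counting excluded patients as non-successes. If half of them recovered, the counts would be 133/171 and 125/171.
- *The plan sets out to drop 20%.* The 80% is a sample-size assumption, not a rule, and the documents do not split it by reason.
- *Nothing planned would reveal the problem.* This cannot be known. The separate statistical analysis plan is not among the documents, and some analyses (relapse, time to switch, baseline summaries) name no set.

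That superiority is tested in mITT is likewise inferred from adjacent sentences. The inference is reasonable, but the text should settle it.

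**Conclusion.** The point holds as a conditional weakness and an inexpensive improvement. In the protocol as written, superiority follows the mITT analysis, the supportive set lies inside mITT, and no efficacy analysis is assigned to RP or ITT. A difference in exclusions between arms biases the superiority test to the extent that excluded patients are non-successes. In the extreme case where all of them are, with 112/171 true success in each arm, a four-point gap in exclusion raises the error from 2.5% to about 14%, and a ten-point gap raises it to about 60%. At the other extreme, with exclusions unrelated to outcome, it stays near 2.5–2.8%. The documents do not say where between these the trial would fall. The stated objective is non-inferiority and superiority is an added step, so the matter should be corrected but does not undermine the main design.

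**What to change.** In the Synopsis and section 12.6.2:

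1. Keep mITT as the primary set for non-inferiority, and name the sets for superiority. Suggested wording: *Superiority will be claimed only if the lower limit of the two-sided 95% confidence interval is above 0 in mITT and also in the Randomized Population, analysed as randomised, with every patient lacking a recorded Visit 4 success counted as a non-success.*
2. Add a sensitivity table with the non-inferiority comparison in the Randomized Population under the same rule.
3. Report exclusions from mITT by arm and by reason, separating failure of criteria 3 and 4, no complete dose, and no efficacy evaluation.

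The cost is a sentence, the added tables and no new data. Superiority becomes somewhat harder to claim, and some excluded patients who recovered will be scored as non-success; the table of reasons lets a reader judge how much that matters. The change should be made before the database is closed, so that the set is not chosen after the results are known.
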